APPENDIX M: Response Assessment in Neuro-Oncology (RANO) Criteria

“Updated Response Assessment Criteria for High-Grade Gliomas: Response Assessment in Neuro-Oncology Working Group”

[figure not shown]

The published criteria may be viewed and/or downloaded by accessing the following website:

<http://ascopubs.org/doi/full/10.1200/JCO.2009.26.3541>

Selection of target lesions:

To evaluate changes in brain tumors using the RANO criteria, up to 5 enhancing lesions identified on baseline T1 (T1 relaxation time constant)-weighted images are measured and monitored for response over time.

Summary of response criteria:

Criterion	Complete Response	Partial Response	Stable Disease	Progressive Disease
T1 enhancing disease	None	$\geq 50\% \downarrow$	$< 50\% \downarrow$ but $< 25\% \uparrow$	$\geq 25\% \uparrow^a$
T2/FLAIR	Stable or \downarrow	Stable or \downarrow	Stable or \downarrow	\uparrow^a
New lesion	None	None	None	Present ^a
Corticosteroids	None	Stable or \downarrow	Stable or \downarrow	NA ^b
Clinical status	Stable or \uparrow	Stable or \uparrow	Stable or \uparrow	\downarrow^a
Requirement for response	All	All	All	Any

Abbreviation: FLAIR = fluid-attenuated inversion recovery; NA=not applicable

a Progression occurs when this criterion is present.

b Increase in corticosteroids alone will not be taken into account in determining progression in the absence of persistent clinical deterioration.

APPENDIX N: iRECIST Response Criteria

“iRECIST: Guidelines for Response Criteria for Use in Trials Testing Immunotherapeutics”

The published criteria may be viewed and/or downloaded by accessing the following website:

http://recist.eortc.org/wp-content/uploads/2017/03/Supplementary-material_iRECIST_Seymour-et-al_revision_FINAL_clean_nov25.pdf

APPENDIX O: NCI Common Terminology Criteria for Adverse Events, Version 4.03

Version 4.03 of the NCI CTCAE, dated 14 June 2010, may be viewed and/or downloaded by accessing the following website:

http://evs.nci.nih.gov/ftp1/CTCAE/CTCAE_4.03_2010-06-14_QuickReference_8.5x11.pdf

1. GLOSSARY OF ABBREVIATIONS

Abbreviation	Description
ATC	anatomical therapeutic chemical
BOR	best overall response
C1D1	cycle 1, day 1
CI	confidence interval
CR	complete response
CTCAE	common terminology criteria for adverse events
DCB	duration of clinical benefit
DCR	disease control rate
DEP	dose escalation phase
DLT	dose-limiting toxicity
DOR	duration of response
ECOG	Eastern Cooperative Oncology Group
EXP	dose expansion phase
ICH	International Conference on Harmonisation
MedDRA	Medical Dictionary for Regulatory Activities
ORR	overall response rate
PD	progressive disease
PFS	Progression-free survival
PR	partial response
PT	preferred term
RECIST	Response Evaluation Criteria in Solid Tumors
SAE	serious adverse event
SAP	statistical analysis plan
SD	stable disease
SI	standard international system of units
SOC	system organ class
TEAE	Treatment-emergent adverse event

Abbreviation	Description
TLF	table, listing and figure
TTR	time to overall response

2. STUDY DESIGN

2.1. BRIEF DESCRIPTION

This is a Phase 1/2a open-label, multi-center, dose-escalation study designed to evaluate the safety, tolerability, PK, PD, and antitumor effects of ALRN-6924 in subjects with advanced solid tumors or lymphomas with WT TP53.

The Phase 1 portion of the study, referred to as the dose escalation phase (DEP), is a “3+3” dose escalation design to establish the MTD and OBD of ALRN-6924. Dose cohorts are delineated in the study protocol.

Two regimens are explored in the Phase 1 portion of the study:

- Dose Regimen A: once weekly for 3 consecutive weeks (Days 1, 8, and 15 of a 28-day cycle)
- Dose Regimen B: twice weekly for 2 consecutive weeks (Days 1, 4, 8, and 11 of a 21-day cycle)

The Phase 2a portion of the study, referred to as the dose expansion phase (EXP), will enroll up to 5 distinct groups of subjects with specific solid tumors and/or lymphomas to further investigate the clinical safety profile and potential efficacy of ALRN-6924 at the MTD or OBD. A third dosing regimen, Dose Regimen C, will also be explored during the EXP. Subjects assigned to this regimen will receive ALRN-6924 on days 1, 3, and 5 of a 21-day cycle.

Treatment of subjects in the dose escalation and the dose expansion phases of the study will continue until documentation of disease progression, unacceptable toxicity, or subject or physician decision to discontinue therapy. Subjects receiving clinical benefit may continue on study after a discussion between the Principle Investigator and Medical Monitor.

2.2. DETERMINATION OF SAMPLE SIZE

The total number of subjects enrolled in the study will depend on the number of dose levels and the number of subjects in each cohort before the MTD or OBD is established. Approximately 75 subjects, exclusive of replacements for subjects who discontinue for non-safety reasons, will be enrolled in the DEP, and approximately 20 additional subjects will be enrolled in each expansion cohort. Enrollment of a total of approximately 175

subjects is planned for the study. Approximately 15 to 25 clinical sites are planned.

2.3. TREATMENT ASSIGNMENT & BLINDING

This is an open-label study. Blinding is not applicable for this study.

3. GENERAL CONSIDERATIONS

3.1. GENERAL METHODS

- This Statistical Analysis Plan (SAP) addresses the analysis methodology for the Phase 1 (dose escalation) portion of this study.
- Separate analysis plans will be developed for analyses of
 - Phase 2a (dose expansion)
 - Pharmacokinetics
 - Pharmacodynamics
 - Cell-free DNA from blood
 - Immunogenicity
- All tabulations of data will be provided by dose cohort within each dose regimen, dose regimen overall, and overall for all subjects in the analysis set.
- Two versions of the 28-day dosing cycle (Dose Regimen A and Dose Regimen A2 as described in the protocol) were implemented in the study, but all analyses will combine these subjects.
- In addition to the tabulations delineated in analysis methods below, all data will be displayed in listings organized by regimen and dose cohort.
- The continuous variables will be summarized using number of observations (n), mean, standard deviation (SD), median, 95% confidence interval of the mean, minimum, and maximum, unless otherwise specified. All mean and median values will be formatted to 1 more decimal place than the measured value. All SD values will be formatted to 2 more decimal places than the measured value. Minimum and maximum values will be presented to the same number of decimal places as the measured value.
- The categorical variables will be summarized using frequency counts and percentages of subjects. Percentages will be calculated using the study population, excluding subjects with missing values, as the denominator. All percentages will be rounded to 1 decimal place. Number and percentage values will be presented as xx (xx.x).

Version V.1

- P-values will be output in the format: “0.xxx”, where xxx is the value rounded to 3 decimal places. Any p-value less than 0.001 will be presented as <0.001. If the p-value should be less than 0.0001, then present as <0.0001. If the p-value is returned as >0.999 then present as >0.999.
- Confidence intervals (CIs) will be presented as 2-sided 95% CIs unless specified differently in specific analyses.
- All analyses will be performed using SAS® statistical software package, version 9.3 or higher.

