Starting at Dose Level (DL) 3 in dose escalation, patients will be sequentially assigned to a treatment arm: Dose Regimen (DR) A will continue testing administration of ALRN-6924 once per week, or Dose Regimen (DR) B testing administration of ALRN-6924 twice per week. For Dose Level 3, DR- A will be enrolled first, DR-B will be enrolled second. The starting dose (DL1) in DEP, based on results from nonclinical toxicology assessments, will be 0.16 mg/kg.

Dose Level and Dose Regimen Schematic – DEP

During the first 2 dose levels, patients will receive ALRN-6924 on Days 1, 8, and 15 of a 28-day cycle. Starting with DL 3, patients in DR- A will continue being treated once a week on Days 1, 8, and 15 of a 28-day cycle, whereas patients in DR- B will be treated twice a week, on Days 1, 4, 8, and 11 of a 21-day cycle. Starting at DL 7A, a modified infusion regimen (DR-A-2) will be explored to mitigate potential infusion reactions.

Treatment Regimen	Infusion Days	Infusion Time	Additional notes
DR-A	1, 8, 15 of a 28-day cycle	1 hour (± 15 min)	At the end of the infusion, IV fluids (saline) or oral fluids (500mL – 1000 mL) should be administered unless clinically contraindicated.
DR-A-2	1, 8, 15 of a 28-day cycle	2 hours (± 15 min)	At the end of the infusion, IV fluids (saline) or oral fluids (500mL – 1000 mL) should be administered unless clinically contraindicated. Administer dexamethasone (4 mg orally or IV) approximately 4 hours after the end of the infusion in Cycles 1 and 2, and thereafter at the discretion of the investigator.
DR-B	1, 4, 8, 11 for DR-B of a 21-day cycle	1 hour (± 15 min)	At the end of the infusion, IV fluids (saline) or oral fluids (500mL – 1000 mL) should be administered unless clinically contraindicated.

A 2-stage dose escalation design will be employed. During the initial Stage 1 Escalation Phase, 100% dose increments will be utilized until ≥ 1 of 3 patients in a cohort experiences any Grade ≥ 2 AE that is at least possibly related to study drug. In Stage 2, dose escalation will continue using 3-patient cohorts and the modified Fibonacci sequence (i.e., 67%, 50%, 40%, 33%), until the MTD or an OBD is established. A drug-related AE is an event that is

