For each phase of study, results will be summarized by dose level and regimen. Tabulations will be produced for appropriate demographic and baseline clinical characteristics, efficacy, pharmacokinetic, and safety parameters. For categorical variables, summary tabulations of the number and percentage of patients within each category of the parameter will be presented. For continuous variables, the number of patients, mean, median, standard deviation, minimum, and maximum values will be presented. Time-to-event data will be summarized using Kaplan-Meier methodology using 25th, 50th (median), and 75th percentiles with associated 2-sided 95% confidence intervals. Graphical displays will be presented, as appropriate. Results will be evaluated for all patients.

TABLE OF CONTENTS

INVESTIGATOR'S SIGNATURE PAGE.....	2
ALRN-6924-1-01 SYNOPSIS.....	3
TABLE OF CONTENTS.....	21
LIST OF TABLES.....	25
LIST OF FIGURES	25
ACRONYM LIST.....	26
1 BACKGROUND AND STUDY RATIONALE	29
1.1 Therapeutic Rationale for Inhibiting MDM2/MDMX to Restore p53 Activity	29
1.2 Stapled Peptide Technology	30
1.3 ALRN-6924.....	30
1.4 Nonclinical Experience with ALRN-6924	30
1.4.1 Pharmacology.....	30
1.4.2 Toxicology and Nonclinical Safety.....	31
1.4.3 Pharmacokinetics and Absorption, Distribution, Metabolism and Excretion	33
1.4.4 ALRN-6924 Administered in Combination with Palbociclib	34
1.5 Clinical Experience with ALRN-6924	41
1.6 Clinical Experience with Palbociclib	41
2 STUDY OBJECTIVES	42
2.1 Phase 1 Dose Escalation (ALRN-6924 administered as single agent therapy)	42
2.1.1 Primary Objectives.....	42
2.1.2 Secondary Objectives	42
2.1.3 Exploratory Objectives.....	42
2.2 Phase 2a Dose Expansion (ALRN-6924 administered as single agent therapy)	42
2.2.1 Primary Objectives.....	42
2.2.2 Secondary Objectives	42
2.2.3 Exploratory Objectives.....	43
2.3 Phase 2a Dose Expansion in MDM2 Amplified or MDM2/CDK4 Co-amplified Solid Tumors (ALRN-6924 plus palbociclib)	43
2.3.1 Primary Objectives.....	43
2.3.2 Secondary Objectives	43
2.3.3 Exploratory Objective	43
3 INVESTIGATIONAL PLAN	44

3.1	Study Rationale	44
3.2	Study Overview.....	44
3.2.1	Pharmacokinetic, Pharmacodynamic, and Clinical Activity Assessments.....	47
3.3	Number of Patients and Centers.....	49
3.4	Duration of Study	49
4	PATIENT POPULATION	50
4.1	Inclusion Criteria – Phase 1 dose escalation (ALRN-6924 administered as single agent therapy)	50

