11. CHANGE FROM ANALYSES PLANNED IN PROTOCOL

This statistical analysis plan is based on protocol Amendment 6, which was finalized on 20 October 2017. In addition to the endpoints outlined in the protocol, duration of clinical benefit has been included as an additional endpoint in this SAP.

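### SAP 3.1 pools Dose Regimens A and A-2 in all analyses, so as worded the level 7 DLT and AE tables may not show which infusion regimen produced which events

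*SAP*

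**What the plan says.** **SAP**

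- Section 3.1 states that the two forms of the 28-day cycle, A and A2, "were implemented in the study, but all analyses will combine these subjects".
- The bullet just before it sets the table layout: "All tabulations of data will be provided by dose cohort within each dose regimen, dose regimen overall, and overall". A later bullet says that "all data will be displayed in listings organized by regimen and dose cohort".
- Section 2.1 introduces the Phase 1 schedules with "Two regimens are explored in the Phase 1 portion of the study" and then lists A and B only.
- Section 11 says "This statistical analysis plan is based on protocol Amendment 6, which was finalized on 20 October 2017". The one difference it reports is: "In addition to the endpoints outlined in the protocol, duration of clinical benefit has been included as an additional endpoint in this SAP".

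**Protocol (supplied version)**

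- Synopsis, Statistical Methods: "For each phase of study, results will be summarized by dose level and regimen". Section 7.3 likewise says that the safety analyses account for every dose level and regimen.
- Synopsis, dose regimen schematic for the DEP: "Starting at DL 7A, a modified infusion regimen (DR-A-2) will be explored to mitigate potential infusion reactions". Section 5.3 gives DR-A a 1-hour infusion. It gives DR-A-2 a 2-hour infusion plus dexamethasone about 4 hours after the infusion ends in Cycles 1 and 2.
- Section 5.5.3 assigns cohorts of three to six separately to DR-A, DR-A-2 and DR-B. Section 6.1 calls the regimens independent of each other.
- Section 5.7.1 records two DLTs at 7A (hypotension; hepatobiliary laboratory abnormalities) and two at 7A-2 (anemia; neutropenia). Each pair is followed by its own stop to escalation.

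**The concern.** DLTs and the MTD are Phase 1 primary objectives (Protocol 2.1.1), and DR-A-2 exists because of infusion reactions. The descriptive result it was added to give is how tolerability looked under the longer infusion with dexamethasone, next to the 1-hour infusion at the same level. A single level 7 column would list four DLT types and one merged AE profile. It would not show that two types arose under one regimen and two under the other. A reader working from the tables would lose that attribution, and nothing in SAP 11 would alert them to it.

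**Working it through.** The plan gives no figure to reproduce. The check is a comparison of the texts, followed by simple proportions.

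**1. Which columns merge?**

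- *Regimen-overall column.* SAP 2.1 counts A and B only and SAP 3.1 combines A with A2, so this column merges them as worded.
- *Level 7 column.* This depends on whether 7A and 7A-2 had the same dose. Protocol 5.7.1 prints 4.4 mg/kg for 7A-2. The 7A dose is not in the text (Figure 9 not shown). Protocol 5.7.2 gives 2.1 mg/kg at DL-5A and 3.1 mg/kg at DL-6A, and the planned steps in 5.7.1 include 50% and 40%:
  - 3.1/2.1 − 1 = 47.6%
  - 4.4/3.1 − 1 = 41.9%; also 3.1 × 1.4 = 4.34

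  Level 7 at 4.4 mg/kg fits that sequence, so equal doses are plausible. This remains an inference.

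**2. What would a pooled level 7 DLT row print?**

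Level 7 cohort sizes are not stated. Assume n patients in the regimen where the event occurred and m in the other, each from 3 to 6 (the range in Protocol 5.5.3), with one patient per DLT type.

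| Quantity | Formula | Range |
|---|---|---|
| Own regimen | 1/n | 1/6 = 16.7% to 1/3 = 33.3% |
| Other regimen | 0/m | 0% |
| Pooled | 1/(n+m) | 1/12 = 8.3% to 1/6 = 16.7% |
| Pooled ÷ own | n/(n+m) | 3/9 = 33% to 6/9 = 67% |

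With equal cohorts, each type prints at half its rate in the regimen where it occurred.

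**3. Vital signs (SAP 8.5)**

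SAP 8.5 summarizes by time point. Protocol Appendix C, footnote 4, takes in-infusion readings at 15 and 30 minutes in DR-A and at 30 and 60 minutes in DR-A-2. The shared 30-minute row therefore mixes infusion stages:

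- DR-A: 30/60 = 50% of the infusion. With ±3 min on the reading and ±15 min on the infusion, 27/75 = 36% to 33/45 = 73%.
- DR-A-2: 30/120 = 25%. With the same windows, 27/135 = 20% to 33/105 = 31%.

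The ranges do not overlap. The end-of-infusion and later readings are timed alike in both regimens, so only this row is affected in that way.

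**The case against.** - **The SAP can be read as keeping the cohorts apart.** Tables are promised by dose cohort within regimen, and the protocol labels 7A and 7A-2 as distinct levels. On that reading only the regimen heading is merged. This stands as a possible reading. The bullet that follows says all analyses, without exception, and so points the other way.
- **The protocol also groups the two.** Section 3.2 puts DR-A and DR-A-2 under one once-weekly schedule, Section 7.1 lists them together, and Appendices C and D cover both. That stands too. It does not remove the separate cohorts, DLTs and stops.
- **The versions differ.** The SAP follows Amendment 6, while the supplied protocol mentions Amendment 7. A reader might infer that the SAP breached the protocol it was written from. The documents do not support that, because the Amendment 6 presentation rule is not available. SAP 3.1 names A2 as a regimen described in the protocol, which shows only that A-2 already existed.
- **The practical effect is limited.** The protocol already attributes all four DLTs, escalation was decided by the Safety Review Committee, and listings remain. This is right as far as decisions go. For reporting, the SAP does not say that A-2 is identified in the listings, and a listing does not replace a summary table on a primary objective.

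**Conclusion.** The point holds as a reporting defect that needs reconciling. The pooling rule merges A and A-2 in the regimen-overall column. It also merges them at level 7 if the two cohorts share a dose and the rule is taken literally. If the doses differ, only the regimen-overall column is affected. The percentages above illustrate the dilution under assumed cohort sizes and do not bound it.

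Three stronger inferences are not supported:

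- *That pooling alters a stop decision.* Both stops are already recorded separately in Protocol 5.7.1.
- *That the pooled DLT rate must stay at 33.3% or more.* This is true for at most six patients per cohort (4/12 = 33.3%). However, the Safety Population (SAP 5.1) is everyone dosed, including patients later replaced (Protocol 4.8), and patients may be added at a level (Protocol 5.7.1). With seven dosed in each cohort and four patients with a DLT, the rate is 4/14 = 28.6%.
- *That the SAP leaves out Cycle 1 DLTs over DLT-evaluable patients.* SAP 8.2 does not state its cycle window, and the protocol uses the term DLT-evaluable without defining it. The inference would rest on silence.

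**What to change.** - Amend SAP 3.1 so that its two bullets agree: 7A and 7A-2 are separate columns in the DLT (8.2), AE (8.3) and vital-sign (8.5) tables, with the pooled 28-day total as supplementary. In 8.5 this also keeps the 30-minute readings apart.
- State that A-2 is identified in the listings.
- Record in SAP 11 any pooling that remains.

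The cost is SAP wording, one extra column at level 7 and a listing label, all from data already collected. The drawback is smaller cells at level 7. The separate columns describe small cohorts treated one after the other and should not be read as a formal comparison.

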3.2. KEY DEFINITIONS**3.2.1. Cycle 1 Day 1**

Cycle 1 Day 1 (C1D1) is defined as the date of the first dose of ALRN-6924.

3.2.1.1. Baseline and Change from Baseline

Baseline value is defined as the last value obtained before the first dose of study treatment administration. This value could be the pre-dose assessment on C1D1 or an assessment obtained during screening. Change from baseline = (post-baseline value - baseline value).

3.2.2. Enrollment

A subject is considered enrolled onto the study after having received at least one dose of study treatment. The enrollment date is set to C1D1.

3.2.3. Study Day and Cycle Day

The study day is the number of days relative to C1D1, while the cycle day is the number of days relative to the first dose date in that cycle. The day of the first dose of ALRN-6924 in Cycle 1 is defined as study Day 1. The day prior to the first dose of ALRN-6924 is study Day -1. There is no study Day 0.

3.3. MISSING DATA

No imputation or extrapolation will be implemented for missing safety or clinical activity results. Partial start/end dates for AEs and medications will be handled as follows:

Adverse events:***Missing day of AE start date***

- AE will be treated as treatment emergent unless the month/year are strictly before the month/year of first dose.

Missing day and month of AE start date

- AE will be treated as treatment emergent unless the year is strictly before the year of first dose.

Missing day, month, and year of AE start date

- AE will be treated as treatment emergent.

Missing any date component of AE end date

- No imputation is needed.

Medications other than study treatment:

Missing any date component of medication start date

- No imputation is needed.

Missing day of medication end date

- Medication will be treated as concomitant unless the month/year are strictly before the month/year of first dose.

Missing day and month of medication end date

- Medication will be treated as concomitant unless the year is strictly before the year of first dose.

Missing day, month, and year of medication end date

- Medication will be treated as concomitant.

3.4. VISIT WINDOWS

All collected lab, vital, and ECG data, including unscheduled visits, will be included in data listings and factored into data analyses though no relabelling of assessments based on visit windows will be instituted. Instead, for summaries by time point, only scheduled assessments will be tabulated according to the visit designations established by investigative sites and cleaned by data management. For shift analyses between baseline and maximum or minimum post-baseline assessments, all assessments, including unscheduled visits, will be included in the identification of extreme values.

3.5. POOLING OF CENTERS

Data from all study centers will be combined for analysis.

3.6. SUBGROUPS

There are no planned analyses by subgroups.

4. STUDY ENDPOINTS

4.1. SAFETY ENDPOINTS

- Treatment emergent adverse events (TEAEs)
 - Dose limiting toxicities (DLTs)
- Laboratory evaluations (hematology, coagulation, chemistry, urinalysis tests)
- Vital signs (systolic and diastolic blood pressure, pulse, respiratory rate, and oral body temperature)
- ECG parameters (overall assessment; heart rate; PR, QRS, QT, and QTc intervals)
- ECOG performance status

4.2. CLINICAL ACTIVITY ENDPOINTS

- Overall response - objective evidence of complete response (CR) or partial response (PR). The evaluation of overall response will be based on response, as determined by the investigator, in accordance with RECIST version 1.1, for subjects with solid tumors, or IWG 2014 criteria, for subjects with lymphomas.

- Overall Response Rate (ORR) - proportion of subjects with overall response
- Time to Response (TTR) - time from the date of the first dose of ALRN-6924 to the date of the first documentation of overall response. The TTR will be calculated as follows (in months):

$$(\text{date of first response (CR/PR)} - \text{first dose date} + 1)/30$$

Subjects who do not respond will be censored at their last tumor assessment.

- Duration of Response (DOR) - time from the first documentation of overall response to the first documentation of objective or clinical disease progression or death due to any cause. This endpoint is only assessed among subjects who achieve overall response at some point during the study. The DOR will be calculated as follows (in months):

$$(\text{date of disease progression/death} - \text{date of first response (either CR or PR)} + 1)/30$$

Version V.1

Subjects who do not have disease progression (or death) will be censored at the last known time point that the subject was progression-free. Subjects with two or more consecutive missing response assessments prior to a visit with progression (or death) will be censored at the last date of tumor assessment when the subject was known to be progression free.

- Disease control - objective evidence of CR, PR, or stable disease (SD). The evaluation of disease control will be based on response, as determined by the investigator, in accordance with RECIST version 1.1, for subjects with solid tumors, and IWG 2014 criteria, for subjects with lymphomas.
 - Disease Control Rate (DCR) - proportion of subjects with objective evidence of disease control
 - Duration of Clinical Benefit (DCB) - time from the first documentation of disease control to the first documentation of objective or clinical disease progression or death due to any cause. This endpoint is only assessed among subjects who achieve disease control at some point during the study. The DCB will be calculated as follows (in months):

(date of disease progression/death - date of first response (either CR/PR/SD) + 1)/30

Subjects who do not have disease progression (or death) will be censored at the last known time point that the subject was progression-free. Subjects with two or more consecutive missing response assessments prior to a visit with progression (or death) will be censored at the last date of tumor assessment when the subject was known to be progression free.

- Best Overall Response (BOR) - the highest level of objective response recorded (complete response, partial response, stable disease, or progressive disease) for each subject
- Progression-free Survival (PFS), defined as the time from the date of the first dose of ALRN-6924 to the date of first evidence of objective or clinical disease progression or the date of death, due to any cause, whichever occurs first. The PFS will be calculated as follows (in months):

(date of disease progression/death - first dose date + 1)/30

Subjects who do not have disease progression (or death) will be censored at the last known time point that the subject was progression-free. Subjects with two or more consecutive missing response assessments prior to a visit with progression (or death) will be censored at the last date of tumor assessment when the subject was known to be progression free.

